### 3.0 STUDY POPULATION

One hundred seventy six (176) HIV-uninfected men and women will be included in this study. A parallel study is being conducted in the US in men who have sex with men; as such, this study aims to enroll a higher proportion of women (60%). Each site will be asked to work with their community advisory boards (CABs) and outreach, education and recruitment teams to develop a recruitment plan appropriate for their local population. Participants will be selected for the study according to the criteria in Sections 3.1 and 3.2. Study participants will be recruited as described in Section 3.3 and assigned to a study arm as described in Section 7.5. Requirements related to participant retention and withdrawal from the study are described in Sections 3.5 and 3.6, respectively. Individual sites will be given enrollment targets and gender distribution targets commensurate with study population needs, adjusted for local epidemiology, such that overall cross-site enrollment meets overall protocol goals. Enrollment targets may be substantially different in terms of gender distribution across sites.

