# 7.0 STATISTICAL CONSIDERATIONS

# 7.1 Review of Study Design

This is a Phase IIa, randomized, multi-site, two-arm, double-blinded study of the safety, tolerability, pharmacokinetics and acceptability of 744LA. Eligible participants will be randomized 3:1, stratified by gender, to receive GSK1265744 or matching placebo. Participants will receive daily 30 mg oral 744 tablets or matching placebo for 4 weeks, followed by a one week washout period, to assess for safety and tolerability prior to receiving injections. Following clinical review of safety lab assessments from the oral regimen phase, participants will enter the injection phase and receive IM injections of 744LA or placebo at three time points at 12 week intervals. IM injections will consist of 800 mg of 744LA or a matching vehicle control, and administered as two 400 mg injections. Participants in the active drug arm will be followed for 52 weeks following their last injection. Participants in the placebo arm will be followed until 52 weeks after their last injection or until the last participant in the active study product arm completes their Week 41 visit, whichever comes first, at which time the study will be unblinded to assess the primary endpoint. When all procedures related to unblinding are completed, participants in the placebo arm will no longer be followed.

176 participants will be randomized 3:1, stratified by gender, as follows:

Arm 1: 132 participants will receive daily oral GSK1265744 (30 mg tablets) for 4 weeks, followed by a one week washout period, to establish safety and tolerability, followed by two IM administered injections of 400 mg (800 mg total) of 744LA at three time points at 12-week intervals as: Week 5, Week 17, and Week 29.

Arm 2: 44 participants will receive daily oral matching placebo and IM injections of vehicle-matched placebo on the same schedule as Arm 1.

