# 7.1.1 Primary Endpoint

Safety endpoint: Proportion of participants experiencing any Grade 2 or higher clinical AEs and laboratory abnormalities that occur from the initial injection to Week 41 among participants who receive at least one injection (injectable phase only)

Tolerability endpoint: Proportion of participants who receive at least 1 injection and who discontinue receiving injections prior to the full course of 3 injections due to intolerability of injection (including but not limited to ISR), frequency of injections, burden of study procedures, or any AE.

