The primary safety endpoint is the proportion of participants experiencing any Grade 2 or higher clinical AEs and laboratory abnormalities that occur from the initial injection to 41 weeks among participants who receive at least one injection. The precision with which the true event rate can be estimated from the observed data depends on the underlying true event rate and the sample size. Table 4 shows the two-sided 95% confidence intervals for the true event rate based on various values for the observed event rates, given the sample size of 120 in 744LA arm and 40 in placebo arm. Calculations are done using the score test method.

Table 4. Two-sided 95% confidence intervals based on observing a particular rate of event for the 744LA arm (n=120) and the placebo arm (n=40)

Observed Event	95% CI (744LA arm)	95% CI (Placebo arm)
Rate (%)		
0	(0, 3.1)	(0, 8.8)
2.5	(0.9, 7.1)	(0.4, 12.9)
5	(2.3, 10.5)	(1.4, 16.5)
10	(5.8, 16.7)	(4, 23.1)
15	(9.7, 22.5)	(7.1, 29.1)
20	(13.8, 28)	(10.5, 34.8)
25	(18.1, 33.4)	(14.2, 40.2)

The safety and toxicity rates of people using 744LA and the rates for those using placebo will not be formally compared. A sample size of 160 participants (120 in 744LA and 40 in placebo) assuming 90% retention rate per year will assure with 82% power that a 95% confidence interval for the difference between the study drug and placebo safety and toxicity rates has an upper limit no more than 10% when the true toxicity rates for 744LA and placebo are both 5%. Table 5 displays two-sided 95% confidence interval for different assumptions on the safety and toxicity rates in the active product and placebo arms for a study of this sample size.

Table 5: Two-sided 95% Confidence Intervals for the Difference between 744LA and Placebo Safety Rates (n=120 in the 744LA arm and n=40 in the placebo arm)

Assumed rate	Assumed rate in 744LA arm											
in placebo arm	1% 5%		7.5%	10.0%	12.5%	15.0%						
1%	(-3.6, 3.6)	(-1, 9)	(0.9, 12.1)	(2.8, 15.2)	(4.8, 18.2)	(6.9, 21.1)						
5%	-	(-7.8, 7.8)	(-5.7, 10.7)	(-3.6, 13.6)	(-1.5, 16.5)	(0.7, 19.3)						
7.5%	-	1	(-9.4, 9.4)	(-7.3, 12.3)	(-5.1, 15.1)	(-2.9, 17.9)						
10.0%				(-10.7,	(05.105)	( ( 2 1 ( 2 )						
	-	-	-	10.7)	(-8.5, 13.5)	(-6.3, 16.3)						
12.5%					(-11.8,							
12.5 /0	-	-	-	-	11.8)	(-9.6, 14.6)						
15.0%						(-12.8,						
15.0 / 0	-	-	-	-	-	12.8)						

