# **Safety Endpoints**

The primary safety analysis will include Grade 2 or higher clinical and laboratory events that occur from the initial injection to 12 weeks after the last injection among participants who receive at least one injection. Secondary safety analyses will include the same definition applied over the oral phase only (week 0 to week 5) and the aggregate oral+injectable+follow-up period.

To assess safety, the number and the percent of participants experiencing each safety endpoint will be tabulated by study arm. Each participant will contribute once in each category (for example, only for the highest severity AE for each participant) for the calculation of event rates. Exact binomial confidence intervals will be calculated for each safety endpoint for each arm and Fisher's exact test used to test for differences in event rates between the two arms. No formal treatment comparisons will be performed in this study, so any p-values that are calculated should only be used as a descriptive statistic. No formal multiple comparison adjustments will be employed for safety endpoints.

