Injectable Hormonal Contraception Usage

Safety and Tolerability analyses described above will be performed on the subset of female participants who self-report the use of injectable hormonal-based contraception at study entry or at any time during the study period. Proportions of such women meeting safety or tolerability endpoints will be compared a) across study arms b) to women in the active study arm who are do not report the use of injectable hormonal contraception c) to the overall study population randomized to active GSK1265744.

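### Comparison (c) in Protocol 7.6.3 sets injectable-contraceptive users against the whole active arm, which contains those same users and the men, so the difference is shrunk and mixed with any sex difference

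*Protocol*

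**What the plan says.** Protocol 7.6.3, under Injectable Hormonal Contraception Usage, applies the safety and tolerability analyses to "the subset of female participants who self-report the use of injectable hormonal-based contraception at study entry or at any time during the study period". The proportions of these women reaching an endpoint are then to be compared in three ways:

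- (a) between the two arms;
- (b) with active-arm women reporting no injectable contraceptive;
- and lastly "c) to the overall study population randomized to active GSK1265744".

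Nothing in (c) takes the users out of the reference group, restricts it to women, or adjusts for the overlap. The evaluation of 744LA in women using hormonal contraception is a listed secondary objective (2.2), and the injectable users have their own secondary endpoint (7.1.2).

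**The concern.** Comparison (c) sets a part against a whole that contains it. An event in an active-arm user counts on both sides, so the two proportions are not independent and their difference is pulled toward zero. The whole also contains the men, while the index group is women only, so any difference between the sexes in event rate enters (c) whether or not contraception matters.

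In a safety analysis, shrinking a difference errs in the less cautious direction. The sex mix can either create a difference or cancel one. The report could then carry two contrasts for the same women, (b) and (c), that disagree for reasons unrelated to contraceptive use.

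**Working it through.** **Inputs from the protocol.** Section 3.0 aims for 60% women. Section 7.1 states: "Eligible participants will be randomized 3:1, stratified by gender, to receive GSK1265744 or matching placebo". About 60% women is therefore expected in the active arm as well. Section 7.2 gives its precision figures "given the sample size of 120 in 744LA arm and 40 in placebo arm". With N = 120 in the active arm, that is 0.60 × 120 = 72 women and 48 men.

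**Inputs assumed.** The protocol gives neither the number of users nor sex-specific event rates. I take users as 15% to 30% of the active arm (18 to 36 of 120), with a wider range of 10% to 40% (12 to 48), and label each event rate below as an assumption. All users are taken to be in the active arm.

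**The plan's own figure.** None is given for (c). The nearest is Table 5 in 7.2, for two separate arms. At 5% in both arms the half-width is 1.96 × √(0.05×0.95/120 + 0.05×0.95/40) = 7.8 points, which matches the stated (−7.8, 7.8). That calculation adds the two variances, which is right for separate groups but not for (c).

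**Step 1: shrinkage.** With m users and f = m/N, the whole-arm proportion is f·p(users) + (1 − f)·p(rest). Hence

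p(users) − p(all) = (1 − f) × [p(users) − p(rest)].

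This is an identity. At f = 0.15 the difference is 85% of the gap to the rest of the arm; at f = 0.30 it is 70%. A true 20-point gap shows as 17 or 14 points.

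**Step 2: sex mix.** If contraception has no effect, users have the women's rate and the expected value of (c) is

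p(women) − [0.60·p(women) + 0.40·p(men)] = 0.40 × [p(women) − p(men)].

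At assumed rates of 30% and 20%, the whole arm is 0.60×30 + 0.40×20 = 26%, so (c) shows 30% against 26%, or +4 points. At 40% and 20% it shows +8.

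Both steps combine as (c) = (1 − f)·[p(users) − p(other women)] + 0.40·[p(other women) − p(men)]. With users 40%, other women 20%, men 50% (assumed) and f = 0.30, this is 0.70×20 + 0.40×(−30) = 14 − 12 = 2 points, where (b) shows 20.

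**Step 3: what a two-sample test would do, if one were used.** Under a common rate p, with q = 1 − p, the true variance of the difference is pq(1/m − 1/N). An independent-samples test assumes pq(1/m + 1/N). The assumed SE is too large by √[(N + m)/(N − m)], so the actual two-sided size at nominal 5% is 2[1 − Φ(1.96 × ratio)].

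| Users of 120 (assumed) | f | 1 − f | SE ratio | Actual size |
|---|---|---|---|---|
| 12 | 0.10 | 0.90 | 1.11 | 3.0% |
| 18 | 0.15 | 0.85 | 1.16 | 2.3% |
| 24 | 0.20 | 0.80 | 1.22 | 1.6% |
| 36 | 0.30 | 0.70 | 1.36 | 0.8% |
| 48 | 0.40 | 0.60 | 1.53 | 0.3% |

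Exact enumeration of the pooled chi-square test, at null rates of 20% and 50%, gives 1.5–1.6% for 24 users and 0.7–0.8% for 36. With users at 40% and everyone else at 20%, power in (c) is 36% for 24 users and 31% for 36. For users against the rest of the arm it is 55% and 64%.

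**The case against.** The best defence is that (c) is only a benchmark. The protocol never says that it estimates a contraceptive effect, and the endpoint in 7.1.2 is simply a proportion. Comparison (b) already gives a women-only contrast without overlap, so a reader can see there whether a difference in (c) reflects sex. The shrinkage factor can be recovered from the reported counts. A spurious 4 points is also small beside the sampling error of the users' proportion: √(0.3×0.7/20) is about 10 points with 20 users, and about 7 with 40. All of this stands, and it keeps the point minor. It does not rescue (c) as a comparison, because the shrinkage and sex mix affect the estimate whatever is done about p-values.

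Three stronger readings are tempting, and the protocol does not support them.

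- *That (c) will be tested at a wrong error rate.* No test is named for (c). Section 7.6.2 has "Fisher's exact test used to test for differences in event rates between the two arms", its chi-square test for tolerability is likewise between the arms, and p-values are descriptive only. The calibration result is conditional, and under a true null the error is toward too few rejections.
- *That never-injected participants enter (c) without a defined outcome.* The word randomized is loose, but 7.6.2 limits the primary analyses to those with at least one injection. Its secondary analyses of the oral phase and the aggregate period do give never-injected participants an outcome.
- *That placebo-arm users are set against 744LA recipients in (b) and (c), diluting the effect by a further quarter.* The index group's arm is not stated, but (a) is the cross-arm contrast and (b) and (c) name active-drug references, so active-arm users are the natural reading. Nor could such a dilution be added to the figures above, which assume that every user is inside the reference group.

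**Conclusion.** The point holds as a low-impact correction to one secondary subgroup comparison. As worded, (c) shows only (1 − f) of the gap between users and the rest of the active arm, 85% to 70% if users are 15% to 30% of it. It also carries 0.40 times any difference between women and men, +4 points at 30% against 20%. The 40% share of men follows from the enrolment target and the stratified allocation; the user share and event rates are assumptions. The overlap identity itself needs no assumption beyond the users being in the active arm.

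The loss of size and power (about 2.3% to 0.8% at nominal 5%) arises only if a standard two-sample test is applied. A reader might infer that the trial's safety conclusion is at risk; it is not. The primary safety and tolerability results by arm do not use (c).

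**What to change.** In 7.6.3:

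1. Drop (c) as a comparison. If the whole active-arm rate is wanted for context, show it beside the users' rate without a difference or a test.
2. Make (b) the contrast for contraceptive use, worded as active-arm users against active-arm female non-users. Use the same analysis population as the endpoint concerned; for the primary safety endpoint that is "from the initial injection to Week 41 among participants who receive at least one injection", and the tolerability endpoint likewise requires at least one injection. Report a difference with 95% CI.
3. Keep (a).

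An interval suits (b) better than a test: with users at 40% and other women at 20%, power is only about 46% with 24 users and 47% with 36. Contraceptive use is not randomized, so (b) remains observational. The cost is a change of about two lines, with no effect on data collection or sample size.

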# 7.6.4 Exploratory Analyses

# Pharmacokinetics/Pharmacodynamics

The relationship between GSK1265744 PK parameters and demography (age, gender, race, ethnicity, weight, BMI, smoking status) or PD endpoints (conversion to HIV-infected status, safety parameters) may be explored.

# Pharmacogenomic Analysis

Specific genes may be studied that encode the drug targets, drug mechanism of action pathways, drug metabolizing enzymes, or drug transporters or which may underpin AEs, disease risk, or pharmacokinetics or drug response. These candidate genes may include a common set of absorption, distribution, metabolism, and excretion genes that are studied to determine the relationship between gene variants and pharmacokinetics or safety parameters. In addition, future research may identify other enzymes, transporters, proteins, or receptors that may be involved in response to GSK1265744. The genes that may code for these proteins may also be studied. Results of any pharmacogenomics investigations performed will be reported either as part of the main clinical study report or as a separate report. A detailed description of any analysis elected to be performed will be documented in the study statistical analysis plan or in a separate pharmacogenomics statistical analysis plan, as appropriate.

### 7.7.5 Interim Analysis/Interim Meta-Analysis

An interim analysis will be performed when 50% of the participants have completed the Week 41 visit. All data available at that time will be included in the analysis. Unblinded summaries from the analysis will be provided to others as pre-specified by the HPTN SMC and to the US FDA. All members of the protocol team, including GSK and ViiV Healthcare, as well as study participants will remain blinded to individual participant treatment assignment. The data from this analysis may also be combined with the interim data from a similar study being conducted by GSK, if needed and appropriate. Pooled summaries will also be provided to the study team to share with regulators. Specifics regarding study monitoring by the SMC and provision of data summaries, their review, and the estimated timing and guidance that will be used to determine regimen safety will be determined by the HPTN SMC, Protocol Chair, and GSK and ViiV Healthcare.

# 8.0 HUMAN SUBJECTS CONSIDERATIONS

#### 8.1 Ethical Review

This protocol and the template informed consent form contained in Appendix VII — and any subsequent modifications — will be reviewed and approved by the HPTN Scientific Review Committee and DAIDS Prevention Science Review Committee with respect to scientific content and compliance with applicable research and human subjects regulations.

The protocol, site-specific informed consent form, participant education and recruitment materials, and other requested documents — and any subsequent modifications — also will be reviewed and approved by the ethical review bodies responsible for oversight of research conducted at the study site.

Subsequent to initial review and approval, the responsible IRBs/ECs will review the protocol at least annually. The Investigator will make safety and progress reports to the IRBs/ECs at least annually, and within three months of study termination or completion. These reports will include

the total number of participants enrolled in the study, the number of participants who completed the study, all changes in the research activity, and all unanticipated problems involving risks to human subjects or others. Study sites are responsible for the submission of continuing review to the DAIDS Protocol Registration Office, in accordance with the current DAIDS Protocol Registration Policy and Procedure Manual.

#### 8.2 Informed Consent

Written informed consent will be obtained from each study participant. Each study site is responsible for developing study informed consent forms for local use, based on the template in Appendix VII that describes the purpose of the study, the procedures to be followed, and the risks and benefits of participation, in accordance with all applicable regulations. If applicable, the study site also is responsible for translating the template form into local languages, and verifying the accuracy of the translation by performing an independent back-translation.

Participants will document their provision of informed consent by signing their informed consent forms. (Further details regarding DAIDS requirements for documenting the informed consent process can be found in the DAIDS Standard Operating Procedure for Source Documentation.)

All participants will be offered a copy of their informed consent form.

#### 8.3 Incentives

Pending IRB approval, participants will be compensated for their time and effort in this study, and/or be reimbursed for travel to study visits and time away from work. Site-specific reimbursement amounts will be specified in the study informed consent forms.

# 8.4 Confidentiality

All study-related information will be stored securely at the study site. All participant information will be stored in locked file cabinets in areas with access limited to study staff. All laboratory specimens, reports, study data collection, process, and administrative forms will be identified by a coded number only to maintain participant confidentiality. All records that contain names or other personal identifiers, such as locator forms and informed consent forms, will be stored separately from study records identified by code number. All local databases will be secured with password-protected access systems. Forms, lists, logbooks, appointment books, and any other listings that link participant ID numbers to other identifying information will be stored in a separate, locked file in an area with limited access.

Participant's study information will not be released without the written permission of the participant, except as necessary for monitoring by the NIAID and/or its contractors; GSK and ViiV Healthcare; representatives of the HPTN LOC, SDMC, and/or LC; the US FDA, OHRP, other government and regulatory authorities, and/or site IRBs.

For sites located in the US, the HPTN will obtain a Certificate of Confidentiality from the US Department of Health and Human Services that will be applicable for this study. Sites may register under the Certificate through the HPTN LOC once they have obtained local IRB approvals for the study. This Certificate protects study staff from being compelled to disclose study-related information by any Federal, State or local civil, criminal, administrative, legislative, or other body.

# 8.5 Communicable Disease Reporting Requirements

Study staff will comply with all applicable local requirements to report communicable diseases identified among study participants to local health authorities. Participants will be made aware of all reporting requirements during the study informed consent process.

### **8.6** Study Discontinuation

The study also may be discontinued at any time by NIAID, the HPTN, the pharmaceutical sponsors, the US FDA, other government or regulatory authorities (OHRP), or site IRBs.

# 9.0 LABORATORY SPECIMENS AND BIOHAZARD CONTAINMENT

Laboratory procedures are described below, Appendices I-III, and Section 5.0; additional tests to be performed at a subsequent visit for participants who have a reactive or positive HIV test result are described in Appendix IV.

# 9.1 Local Laboratory Specimens

The following types of tests will be performed at the local laboratory:

- HIV testing (see SSP Manual)
- HBV and HCV testing to include hepatitis B surface antigen (HBsAg), hepatitis B surface antibody (HBsAb), hepatitis B core antibody (HBcAb) and hepatitis C antibody (HCV) tests
- CBC with differential and platelets
- Chemistry testing (BUN/urea, Na, K, Cl, CO2, CPK, creatinine, total protein, glucose, calcium, phosphorous, amylase, lipase, magnesium)
- LFTs (AST, ALT, total bilirubin, alkaline phosphatase)
- Fasting lipid profile (total cholesterol, HDL, triglycerides, LDL calculated or measured (participants should be fasting for at least 8 [preferably 12] hours prior to sample collection)
- Syphilis serologic testing (men and women)
- Urine for GC/CT testing for men and women. (may be replaced with a vaginal swab in women if desired)
- Urinalysis (protein and glucose)
- Urine test for pregnancy\*
- Rectal swabs for GC/CT for men and women (for non-US sites, batch and ship to the HPTN LC; for US sites, testing will be performed locally)
- Plasma storage
- Plasma storage for Pharmacology testing
- Sample storage for Pharmacogenomic testing
- Following a positive or reactive HIV test result: HIV viral load, CD4 cell count, HIV resistance testing at a local laboratory (optional, at the site's discretion, for clinical management), plasma storage.

If the HIV testing algorithm includes HIV rapid testing, that testing may be performed in the clinic or laboratory. Urine pregnancy testing may be performed in the clinic or the laboratory.

\*All women of reproductive potential will have a urine  $\beta$ HCG test for pregnancy (sensitivity of  $\leq$  25 mIU/mL) at each visit. Pregnancy testing is not required at subsequent visits if a woman had a positive pregnancy test at a previous visit and is still pregnant.

Each study site will adhere to standards of good laboratory practice, the HPTN LC Manual, the SSP and local SOPs for proper collection, processing, labeling, transport, and storage of specimens to the local laboratory. Specimen collection, testing, and storage at the local laboratory will be documented using the HPTN Laboratory Data Management System (LDMS) as described in the SSP Manual.

All specimens will be shipped in accordance with International Air Transport Association (IATA) specimen shipping regulations. All shipments will be documented using the HPTN LDMS as described in the SSP Manual.

